### **15.3 Specific Aim 2 Analysis**

It is hypothesized that participants randomized to GLB+ will on average maintain  $\geq 7\%$  weight loss at 12- and 18-months compared to participants randomized to GLB, who are expected to maintain an average loss of 5%. A multiple regression model using the matched pair design described above will be employed in two ways: first, using the percent change at 12- and 18-months as repeated measures nested within matched pairs, and second, as absolute changes using baseline, 12-, and 18-month weights. Significant covariates chosen will be incorporated into these models.

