## **2.0 Brief Overview of the Study Protocol**

The purpose of this study is to implement and evaluate a lifestyle intervention for Ohio State University (OSU) employees with prediabetes to determine the impact of the intervention on weight loss and related outcomes to reduce risk for type 2 diabetes mellitus (T2DM). People with prediabetes are at high risk for progressing to T2DM, and weight loss is the most effective treatment for risk reduction. This study trial follows a preliminary trial to evaluate the efficacy of a lifestyle intervention implemented at a university worksite. The efficacy trial was highly successful in promoting weight loss on average among participants randomized to the experimental group. However, about 50% of experimental participants did not achieve clinically meaningful weight loss. More effective treatments are needed for people who are slower to respond to behavioral interventions. A goal of this trial is to determine whether augmented care for slow responders promotes greater weight loss and risk reduction. Effective weight loss maintenance interventions also are needed to reduce risk for T2DM. We will examine the impact of an extended intervention phase on weight loss maintenance following an intensive lifestyle intervention.

The specific aims of this translational study at a university worksite are to:

**Specific Aim 1:** Implement the first 4-sessions of the core 16-session phase of the Group Lifestyle Balance (GLB) intervention for diabetes prevention to all study participants. GLB is the group-based version of the intervention implemented in the Diabetes Prevention Program. Determine percent weight change at week 5. Provide a 12-session augmented intervention (called Group Lifestyle Balance Plus (GLB+)) to participants who fail to achieve > 2.5% weight loss at week 5; provide the remainder of the 12-session standard GLB intervention to all other participants. GLB+ will be enhanced with training in values clarification, mindful decision making, planning, and problem solving. Evaluate the impact of the augmented GLB+ intervention to the standard GLB intervention immediately following the core intervention phase (4 months from baseline).

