**Specific Aim 2:** Create matched pairs of participants based on sex and percent weight change at 4-months following the core intervention phase. Randomly assign each person in the pair to either the standard GLB intervention or to the augmented GLB+ intervention for the 8-month extended intervention phase. Evaluate the impact of the GLB+/GLB+ intervention sequence to the GLB/GLB intervention sequence at 12- and 18-month follow-up. One exploratory sub-aim will be to identify optimal treatment sequences embedded in the adaptive design on percent weight change at 18 months.

**Specific Aim 3:** Estimate the costs and cost-effectiveness of each intervention from a health system and societal perspective.

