### **4.0 Study Flow Diagram**

An overview of the general study processes is provided in Figure 1. In this trial, participants are not randomized to treatment group at baseline. Instead, all participants receive the first four weeks of the standard GLB intervention. During these first four weeks, participants learn basic skills such as self-monitoring, the calorie and fat content of food and beverages, and how to initiate a physical activity program such as brisk walking. Participants then remain in the standard GLB intervention if they achieve at least 2.5% weight loss at week 5. If participants do not achieve this level of weight loss, they will be stratified to the augmented GLB+ intervention at week 5. Participants will be randomized to treatment group following the core intervention phase (first 16 weeks) for the extended (8 months) and maintenance (6 months) intervention phases.

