## **7.0 Research Design and Study Intervention**

Following baseline data collection, all participants will begin the 16-session core phase of the Group Lifestyle Balance (GLB) intervention. Percent weight change will be determined at the beginning of week 5, after 1 month of intervention. Those who achieve  $> 2.5\%$  weight loss will complete the remainder of the 12 GLB sessions. Those who achieve  $\leq 2.5\%$  weight loss will be stratified to the Group Lifestyle Balance Plus (GLB+) intervention (additional 12 sessions). A second round of data collection will

occur upon completion of the core intervention study phase, 4 months from baseline. Following this second data collection, participants will be matched into pairs based on gender and percent weight change at 4 months, and each person in a matched pair will be randomly assigned to treatment group for the extended intervention study phase. One person in each pair will receive either the standard GLB intervention or the augmented GLB+ intervention, and the second person in each pair will receive the alternate intervention. Following completion of the extended intervention study phase at 12 months, a third round of data collection will occur. A 6-month no contact phase will follow the extended intervention study phase to evaluate weight loss maintenance. The fourth and final round of data collection will occur upon completion of the 6-month no contact phase, 18 months from baseline.

The goals of both the GLB and GLB+ interventions include losing  $\geq 7\%$  of initial body weight and maintaining  $\geq 7\%$  weight loss through study end. The intervention group sessions will consist of 10-15 participants (to foster

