## **8.0 Randomization**

Participants will be randomly assigned to treatment group following the 16-week core intervention phase. Participants will be matched, based on gender and percent weight change following the 4-month data collection visit. Each person in a matched pair will be randomly assigned to either the GLB or the GLB+ intervention for the extended and maintenance intervention phases. The biostatistician will create the randomization log and will be blinded to treatment group during the core intervention phase.

- **Process Responsibilities:** The Study Coordinator will maintain the master randomization list from the statistician. The Study Coordinator will be responsible for assigning randomization codes, notifying appropriate study staff that the participant has been randomized, and securely storing all randomization files.

The assigned and blinded randomization code, that is separate from study data, will be kept in a paper-based randomization log in a locked filing cabinet.

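### Aim 2 pools two different randomised contrasts, adding GLB+ in early responders and continuing it in slow responders, with no prespecified core-arm term or interaction

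*Combined protocol and SAP*

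**What the plan says.** **Before randomisation.** All participants receive four GLB sessions. Section 4.0 then states: "If participants do not achieve this level of weight loss, they will be stratified to the augmented GLB+ intervention at week 5". Section 7.0 gives this group 12 GLB+ sessions; the others complete 12 more GLB sessions. Core treatment is therefore set by week-5 response.

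**Randomisation.** Section 8.0: "Participants will be randomly assigned to treatment group following the 16-week core intervention phase". Section 7.0 says that "participants will be matched into pairs based on gender and percent weight change at 4 months", and one member of each pair goes to each extended arm. Sections 2.0 and 8.0 name the same two matching variables. Core arm is not one of them.

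**Aim 2 analysis.** Section 15.3 expects an average loss of at least 7% in those randomised to GLB+ and 5% in those randomised to GLB, at 12 and 18 months. "A multiple regression model using the matched pair design described above will be employed in two ways": percent changes as repeated measures within pairs, and absolute weights. Covariates enter if significant. Core arm and a core-by-extended interaction are not named.

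**Four sequences.** The table at the end of Section 15.4.2 lists A (GLB then GLB), B (GLB then GLB+), C (GLB+ then GLB) and D (GLB+ then GLB+). The section on comparing treatment sequences, also numbered 15.4, sets an exploratory analysis of covariance at 18 months with an F-test and Tukey comparisons. Its main comparison is A against D. It also says the trial will determine whether extended GLB+ is best for early non-responders and whether early responders need it.

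**The concern.** The GLB arm of Aim 2 holds two kinds of participant: early responders who never had GLB+ and slow responders who have just finished 12 sessions of it. GLB+ teaches skills such as planning and problem solving, and a participant may keep using them after moving to GLB. The effect of extended GLB+ could therefore differ between the groups, and one pooled coefficient would not show it.

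Two readings of the result are at risk. A pooled null could be taken to mean that extended GLB+ helps nobody, although it might help those new to it. A pooled positive could be taken as evidence for slow responders, whom Section 2.0 singles out: "A goal of this trial is to determine whether augmented care for slow responders promotes greater weight loss and risk reduction". Core GLB+ is assigned by response, so D against C is the only randomised evidence on GLB+ in slow responders. The plan gives it no prespecified estimate at 12 months and only exploratory standing at 18. The cost-effectiveness ratio in Section 15.4, which compares the extended arms, inherits the same mixture.

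**Working it through.** The documents give no sample size, standard deviation, power, slow-responder share or carry-over figure, so there is no plan figure to reproduce.

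**1. Planned GLB+ sessions by sequence** (Sections 7.0 and 15.4.2). The extended phase has 2 + 7 = 9 sessions.

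| Sequence | Core GLB+ | Extended GLB+ | Total |
|---|---|---|---|
| A | 0 | 0 | 0 |
| B | 0 | 9 | 9 |
| C | 12 | 0 | 12 |
| D | 12 | 9 | 21 |

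B − A and D − C each add 9 sessions, but from a starting point of 0 in one case and 12 in the other.

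**2. What the pooled effect is.** With s the share of slow responders:

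pooled = (1 − s)(B − A) + s(D − C).

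Section 15.3 states its 7% and 5% for everyone randomised, so 7 − 5 = 2 points (at least) is already the pooled effect. Put D − C = k(B − A). Then B − A = 2 / [(1 − s) + ks]. Both s and k are assumptions. The nearest figure to s in the documents is the roughly 50% in the preliminary trial, on a different criterion.

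| k | s = 0.3: B − A, D − C | s = 0.5: B − A, D − C | s = 0.6: B − A, D − C |
|---|---|---|---|
| 0 | 2.86, 0 | 4.00, 0 | 5.00, 0 |
| 0.5 | 2.35, 1.18 | 2.67, 1.33 | 2.86, 1.43 |
| 1 | 2.00, 2.00 | 2.00, 2.00 | 2.00, 2.00 |
| 1.25 | 1.86, 2.33 | 1.78, 2.22 | 1.74, 2.17 |

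Every row gives the same pooled 2 points.

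**3. Does matching without core arm bias the comparison?** In a pair that mixes core arms, the coin toss gives either D − A or B − C. The expected difference is ½[(D − A) + (B − C)] = ½[(B − A) + (D − C)], an average of the two randomised effects. A simulation of the pairing rule (assumed 240 participants, 25% men, SD 4 for 4-month change, core-arm gap 0 to 4 points, s from 0.3 to 0.6) gave 34% to 50% mixed pairs. Mean core-arm imbalance between extended arms was about 0, with SD about 5 to 7 percentage points. Other assumptions (200 participants, week-5 to month-4 correlation 0.5 to 0.8) gave 27% to 42% mixed pairs. The cost is precision and chance imbalance.

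**4. The sequence analysis.** Four groups give six Tukey pairs, of which B − A and D − C are the two randomised within core arm. The comparison named as primary splits as D − A = (D − C) + (C − A). The second term sets slow responders against early responders with different core treatment, so randomisation does not protect it. Aim 2 in Section 2.0 uses this same A-against-D wording for 12 and 18 months, whereas Section 15.3 tests the randomised extended arms.

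**5. Precision of separate effects.** With equal residual variance and 1:1 allocation within core arm, SE(stratum) = SE(pooled) / √share. At s = 0.5 this is 1/√0.5 = 1.41 times the pooled SE. For s from 0.3 to 0.6 it runs from 1/√0.7 = 1.20 to 1/√0.3 = 1.83. The interaction has √[1/s + 1/(1 − s)] times the pooled SE: 2.00 at s = 0.5, 2.04 at 0.6 and 2.18 at 0.3.

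**The case against.** The strongest reply is that core treatment precedes randomisation and is the same by design in both extended arms. Any difference by core history is then effect modification, and the pooled contrast remains a sound average effect. That stands. The four sequences are also declared openly, the question about early non-responders is already posed, and keeping subgroup contrasts exploratory is defensible when no power is stated for them. Most of that stands too. It does not explain why the two randomised contrasts have no 12-month estimate, or why the lead comparison is the non-randomised one.

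It can also be said that the slow-responder goal belongs to Aim 1 at month 4, not to Aim 2. That is a fair reading of Section 2.0. But the Aim 1 comparison is between groups formed by response, and the sequence section raises the slow-responder question again for the extended phase.

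A reader might go further and infer that carry-over dilutes the pooled effect, for example from 2 points to 1.5 or 1.0, so that 1.8 or 4 times the sample is needed. The documents do not support this. Those figures require the 2 points to be the effect in early responders alone, whereas Section 15.3 states them for all randomised. No carry-over is documented, and the effect in slow responders could be smaller, equal or larger. A reader might also infer that pairing across core arms biases Aim 2; step 3 of the working shows that it does not.

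**Conclusion.** The point holds as one of interpretation and reporting. Section 15.3 pools two distinct randomised contrasts and prespecifies nothing that separates them, while the plan promises an answer for each group. The pooled estimate is unbiased for the average over core histories.

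No dilution figure should be claimed. Under the assumed shares of 0.3 to 0.6, a pooled 2 points is compatible with anything from no effect in slow responders and 2.86 to 5.00 points in early responders, through equal effects, to a somewhat larger effect in slow responders. That range shows what the pooled number leaves open; it does not predict the result. The session counts are planned, not attended.

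The conflict between the Aim 2 wording in Section 2.0 and the contrast in Section 15.3 rests on no assumption: the former is confounded by week-5 response and the latter is randomised.

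**What to change.** 1. In Section 15.3, include core arm as a prespecified fixed covariate whatever its significance. It is fixed at week 5, before randomisation, so adjusting for it is legitimate.
2. Add the core arm by extended arm interaction. Report B − A and D − C with confidence intervals at 12 and 18 months beside the pooled effect.
3. State the question that D − C answers: whether, in slow responders, continuing GLB+ rather than moving to GLB after month 4 improves weight at 12 and 18 months.
4. Reconcile the Aim 2 wording in Section 2.0 with Section 15.3, and label any A-against-D comparison as non-randomised.
5. Reconcile Section 4.0 with Section 7.0 for a loss of exactly 2.5%, which they place in different core arms, so that the core-arm variable has one definition.

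Pairing within core arm is optional, where the pairing pool is large enough. Section 7.0 describes groups of 10 to 15. If pairs were formed within such a group, then with an assumed 25% minority sex and half slow responders, each cell of that sex would hold about 10 × 0.25 × 0.5 = 1.25 to 15 × 0.25 × 0.5 = 1.9 people. The model terms do not depend on this and can be added even if pairing is complete.

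**Cost.** Core arm is already on file; no visits, participants or treatments change. The separate effects have wider intervals than the pooled one, so they should be read as estimates. A non-significant interaction should not be taken as proof of equal effects.

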social support) and will be  $\sim 60$  minutes in length held during the noon hour or immediately after work to accommodate participants' work schedules. Those who miss a group session will be encouraged to attend a make-up session prior to the next regularly scheduled session. Approximately 15-20 cohorts of participants will complete the study, and several groups of participants will run concurrently for staffing purposes. Each participant will receive a copy of the weekly printed handouts, a fat and calorie counter, self-monitoring booklets, and a chart for recording body weight. Self-monitoring is a key strategy used during the intervention to promote self-regulation and goal attainment. Participants will be encouraged to self-monitor fat and calorie intake daily, to record their weekly minutes of PA, and to self-weigh (1 day/week in GLB). The monitoring records will be reviewed by the lifestyle coaches weekly with personalized feedback provided to participants.

Following completion of the 16-week core intervention phase, participants will enter the 8-month extended intervention phase. The extended phase will consist of 2 bimonthly group sessions followed by 7 monthly group sessions. The content presented will reinforce skills needed to achieve and maintain the behavioral goals. In addition, we will encourage continued goal attainment through individual goal setting, self-weighing, and social support. Participants will be encouraged to continue to self-monitor periodically (e.g., once/month) and to submit monitoring records for review. Finally, the 6-month maintenance phase of the study that follows the extended intervention phase will include no contact from program staff to assess sustainability of program outcomes.

When a participant does not attend a regularly scheduled group session, a make-up session will be scheduled for that person. The lifestyle coach will contact the participant to determine the reason for the missed session and to remind the individual to attend a

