## **13.2 Quality Control Procedures**

All study personnel, including undergraduate assistants, will complete training in the ethical conduct of human subjects' research through the Office of Responsible Research Practice at OSU prior to joining the study. This training will include the CITI training modules, the 9 Good Clinical Practice training modules, and the training modules for the Responsible Conduct of Research. IRB training will be renewed every 3 years. Lifestyle coaches for the intervention also will complete the 2-day training for the Group Lifestyle Balance curriculum led by [name] from the University of Arizona. Training in the GLB+ curriculum for the coaches will be led by Drs. [name], [name], and [name].

At least 20% of the intervention sessions will be randomly selected and audio recorded for intervention fidelity. Participants will provide consent for the recording process. The observer will complete the Intervention Fidelity Checklist, indicating whether the intervention was implemented as planned within 2 weeks of the intervention session. No personally identifying information will be included on the Fidelity checklist. The document will be reviewed by [name] as soon as it is completed. Departures from the intervention curriculum will be discussed with program staff and additional training will be provided as needed.

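### If extended-phase session groups are single-arm and carry outcome variance that pair mates do not share, the Aim 2 models, which state only matched pairs, understate the standard error of GLB+ minus GLB

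*Combined protocol and SAP*

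**What the plan says.** Participants are randomised individually within matched pairs after the 4-month visit. Section 7.0 says that one member receives GLB or GLB+ and that "the second person in each pair will receive the alternate intervention".

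Treatment is delivered in groups. Section 7.0: "The intervention group sessions will consist of 10-15 participants", a size chosen for social support. For the randomised phase: "The extended phase will consist of 2 bimonthly group sessions followed by 7 monthly group sessions". On numbers: "Approximately 15-20 cohorts of participants will complete the study, and several groups of participants will run concurrently for staffing purposes".

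Section 15.3 gives the Aim 2 model in a relative and an absolute form. The relative form is fitted "using the percent change at 12- and 18-months as repeated measures nested within matched pairs". The absolute form is described only briefly, and its wording leaves open how baseline weight enters: "second, as absolute changes using baseline, 12-, and 18-month weights". Covariates found significant are added. Neither model has a term for session group, cohort or coach. Section 15.1 names PROC MIXED but no random effects. No section gives an ICC or a plan for clustering by group.

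The arm composition of extended-phase groups is not stated. Two places bear on it. Section 2.0: "GLB+ will be enhanced with training in values clarification, mindful decision making, planning, and problem solving", and its Aim 2 assigns GLB+ as an extended-phase treatment. Section 13.2 describes separate coach preparation: "Training in the GLB+ curriculum for the coaches will be led by" named study personnel. Whether pairs are matched within cohort is not stated either.

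**The concern.** People who meet in one group share a coach, a time slot and each other's support, so their outcomes may be correlated. A model that knows only about pairs treats members of one session group as independent, apart from the pairing. If each group belongs to one arm, pair mates sit in different groups. Any group effect that they do not share then stays in the pair difference and does not average out at the rate that the model assumes.

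Aim 2 is the trial's only randomised comparison, with an expected gap of about 2 points (at least 7% against 5% loss, section 15.3). With too small a standard error, a few groups that happened to do well could be read as a GLB+ benefit.

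**Working it through.** The plan states no sample size, SD, power or standard error for Aim 2, so there is no planned figure to reproduce.

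**Inputs from the documents.** Group size m = 10-15 (section 7.0); 1:1 allocation within pairs (sections 7.0 and 8.0).

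**Assumptions.** Two-sided 5% test (section 15.2 gives 0.05 for Aim 1 only); single-arm groups; unshared ICC 0.01-0.05; pair correlation ρ 0-0.5. Groups of 5-8 are added in case cohorts are split by arm.

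**Formula.** Take n pairs and total variance σ², with ρ and ICC as shares of it. Suppose pair mates sit in groups with independent effects.

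- Variance reported by the pair-only model: 2σ²(1−ρ)/n.
- True variance: 2σ²[(1−ρ) + (m−1)·ICC]/n.
- Design effect: DEFF = 1 + (m−1)·ICC/(1−ρ).
- True SE / reported SE = √DEFF. Type I error = 2[1 − Φ(1.96/√DEFF)].

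| m | ICC | ρ | DEFF | true/reported SE | type I error |
|---|---|---|---|---|---|
| 5 | 0.01 | 0 | 1 + 4×0.01 = 1.04 | 1.02 | 5.5% |
| 8 | 0.01 | 0.5 | 1 + 7×0.02 = 1.14 | 1.07 | 6.6% |
| 10 | 0.01 | 0 | 1 + 9×0.01 = 1.09 | 1.04 | 6.0% |
| 15 | 0.01 | 0.5 | 1 + 14×0.02 = 1.28 | 1.13 | 8.3% |
| 8 | 0.05 | 0.5 | 1 + 7×0.10 = 1.70 | 1.30 | 13.3% |
| 15 | 0.05 | 0.5 | 1 + 14×0.10 = 2.40 | 1.55 | 20.6% |

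**Simulation of the percent-change model** (pairs spread at random over single-arm groups, tests at each visit, 1,500 runs per cell). With m 10-15 the pair-only analysis rejects 5.7-8.0% at ICC 0.01 and 10.7-21.1% at ICC 0.05. With m 5-8 it rejects 4.7-7.9% and 7.2-11.5%. At ICC 0 it rejects 4.1-5.3%.

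**If pair mates share part of the group effect.** Suppose pairs are matched within cohort and sit in parallel groups. Let s be the part of the ICC that they share and u the rest. The shared part cancels in the difference, so DEFF = 1 + (m−1)·u/(1−ρ−s). With half of 0.05 shared (u = s = 0.025) and ρ = 0.5:

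- m = 15: 1 + 14×0.025/0.475 = 1.74, type I error 13.7% (13.5% in simulation).
- m = 8: 1 + 7×0.025/0.475 = 1.37, type I error 9.4% (9.5% in simulation).

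With half of 0.01 shared, the simulated range over all cells is 5.0-6.6%.

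**Control.** When correlated groups cross the arms (m 10-15, 6,000 runs per cell), true/reported SE is 0.995-1.015 and rejection 5.0-5.2%.

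**The case against.** The strongest reply is that the defect depends on two facts that the documents do not state. The GLB+ content in section 2.0 is introduced with the core phase, the coach training in section 13.2 is tied to no phase, and section 7.0 gives one schedule and one content description for the whole extended phase. This stands as far as it goes: group composition is a gap in the text, and single-arm groups are an inference. It does not remove the point, because Aim 2 assigns GLB+ as an extended-phase treatment.

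Second, pairing may absorb part of the group effect. This stands. A reader might infer that any correlation within groups is enough to invalidate the standard error. The documents do not support that: they leave open whether pairs are matched within cohort, and season, calendar time or a coach common to parallel groups would then cancel. Only the variance that pair mates do not share matters.

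Third, the ICC may be low. Nine sessions in 8 months, individual make-up sessions and 6 months without contact before month 18 all point that way. This also stands, most of all for month 18. A reader might take 20.6% as the expected error; it needs 15 per group, unshared ICC 0.05 and pair correlation 0.5 together.

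A reader might also extend the point to the core-phase groups. These were formed before randomisation and can cross the arms, so they do not by themselves understate this standard error. No claim is made about the exploratory comparison of treatment sequences.

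Finally, a group term costs precision and could be kept as a sensitivity analysis. The cost is real and is set out under the fix. But if groups are single-arm, leaving the term out of the main model makes its validity depend on an unshared ICC of about 0.

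**Conclusion.** The point holds conditionally. If extended-phase groups are single-arm and there is group-level variance that pair mates do not share, both Aim 2 models as written give too small a standard error for GLB+ minus GLB, and type I error is above nominal. If either condition fails, there is no problem.

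The size rests on assumed values throughout. It is small at an unshared ICC of 0.01 and material at 0.05, less so if pair mates share part of that ICC. Month 12 may be affected more than month 18. The matter should be settled before analysis, with medium confidence, because the deciding fact is one that the sponsor knows and the documents omit.

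**What to change.** In section 7.0, state whether extended-phase groups are single-arm and whether pairs are matched within cohort. Record each participant's extended-phase session-group ID; without it, clustering cannot be examined later.

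If groups are single-arm, add to section 15.3:

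> Both Aim 2 models will include a random effect for extended-phase session group, in addition to the matched-pair effect, applied to the 12- and 18-month visits and allowed to differ in variance by visit (reduced to a common intercept if it does not converge), with Satterthwaite degrees of freedom. The ICC at each visit will be reported.

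Two details matter:

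- **Visits.** Section 15.3 does not say whether baseline weight enters the absolute-change model as a response. If it does, a time-constant group intercept cancels from the arm-by-time contrast. In simulation (m 10-15, ICC 0.01-0.05) it left rejection at 5.4-20.1%, the same as with no group term; an effect on months 12 and 18 only gave 3.3-5.6%.
- **Variance by visit.** With ICC 0.05 at month 12 and 0.01 at month 18 (m 10-15), a common intercept in the percent-change model rejected 5.3-7.2% and 1.8-3.6%, against 11.1-19.3% and 6.5-8.3% for pairs only. The version with variance by visit was not itself simulated.

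The cost is one ID variable and one random effect, crossed with pairs, in PROC MIXED. Intervals widen and degrees of freedom fall. With a common intercept in the percent-change model, the mean SE rose 7-12% at ICC 0, 8-19% at 0.01 and 12-53% at 0.05. Median degrees of freedom at ICC 0.01-0.05 were 8-12 with 8-10 groups per arm and 14-23 with 15-20. Type I error was 2.5-5.4% at ICC 0.01-0.05 and 2.3-3.9% at ICC 0, so the test is somewhat conservative when there is little clustering. Loss of power was not quantified.

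### Aim 2 uses the month-4 result only through the matched pairs; naming it as a fixed covariate in both models would be a free, modest gain in precision

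*Combined protocol and SAP*

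**What the plan says.** The second round of data collection is to "occur upon completion of the core intervention study phase, 4 months from baseline" (section 7.0), and randomisation comes after it. Section 8.0 states: "Participants will be matched, based on gender and percent weight change following the 4-month data collection visit". The Aim 2 statement in section 2.0 gives the same two matching factors. Within a pair, one person gets GLB or GLB+ and "the second person in each pair will receive the alternate intervention" (section 7.0).

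For the analysis, section 15.3 states: "A multiple regression model using the matched pair design described above will be employed in two ways". The first way takes percent change at 12 and 18 months as repeated measures nested within pairs. The second is "as absolute changes using baseline, 12-, and 18-month weights". The only rule for other covariates is: "Significant covariates chosen will be incorporated into these models".

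The documents do not say how close a match must be, or whether pairs are formed across the whole trial, within a recruitment wave or within a cohort. They do say "Approximately 15-20 cohorts of participants will complete the study" and that several groups run at the same time (section 7.0).

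**The concern.** In a trial randomised at month 4, the month-4 value is the natural baseline for the randomised comparison and is likely to be a strong predictor of weight at 12 and 18 months. Neither Aim 2 model includes it by rule. It enters only indirectly, through the pair, or by chance, if it happens to pass a significance screen.

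The pair carries the month-4 information only as well as the match is close. Three gaps remain:

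- Pair members may differ at month 4, especially if the matching pool is small and split by sex.
- Matching on percent change does not match on kilograms, which is the scale of the second model.
- A person left unpaired, or whose partner is lost in the 14 months after randomisation (18 − 4), has no pair to carry the month-4 value.

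At stake is the width of the confidence interval for the randomised comparison.

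**Working it through.** **What the documents supply.** The timing of randomisation, the matching factors, 1:1 assignment within pairs, and the weights named for the model. They give no sample size, SD, correlation, power, matching pool or closeness rule, so there is no planned figure to reproduce. All sizes below rest on assumed inputs.

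**Step 1. What adjustment can still gain once pairs are kept.** Let ρ be the correlation between month-4 and later percent change. Let m be the mean squared within-pair difference in month-4 percent change, divided by twice its variance (m = 0 for perfect matching, m = 1 for random pairing). In units of twice the outcome variance, the variance of a within-pair outcome difference is ρ²m + (1 − ρ²). Adjusting for the month-4 value leaves 1 − ρ². So:

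R = (1 − ρ²) / (ρ²m + 1 − ρ²), and the cut in standard error is 1 − √R.

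With ρ = 0.7 and no matching (m = 1), R = 1 − 0.49 = 0.51. Simulation of an unmatched trial with absolute change as outcome gave 0.54-0.55. That would be the loss if the month-4 result were not used at all, which is not this plan.

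**Step 2. Simulated variance ratios with pairs and baseline weight in both models.** Assumptions: N of 150, 220 or 300; baseline weight about 95 kg, SD 18; SD of change 4.5% at month 4 and 7% at follow-up; ρ = 0.7; 1,500 trials per setting.

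| Matching pool | R | SE cut, 1 − √R |
|---|---|---|
| Whole trial | 0.97-0.98 | 1.0-1.5% |
| Waves of 40 | 0.90-0.94 | 3-5% |
| Groups of 12 | 0.79-0.81 | 10-11% |

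Solving Step 1 for m, m = (1 − ρ²)(1/R − 1)/ρ². For R = 0.80 this is 0.51 × 0.25 / 0.49 = 0.26; for R = 0.92, 0.51 × 0.087 / 0.49 = 0.09; for R = 0.975, 0.51 × 0.0256 / 0.49 = 0.03. Even the loosest pairing considered already removes roughly three quarters of the month-4 variation from the comparison.

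Over ρ from 0.5 to 0.8, R runs from 0.94 to 1.01 trial-wide, 0.83 to 0.98 in waves of 40, and 0.65 to 0.94 in groups of 12.

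**Step 3. The two follow-up visits separately.** Assumptions: N = 200, 25% men, correlations 0.75 (12 months) and 0.65 (18 months). The table shows the SE cut for the absolute-change difference from adding month-4 weight to a paired model that already has baseline weight.

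| Matching pool | 12 months | 18 months |
|---|---|---|
| 12 | 14% | 9% |
| 25 | 6% | 4% |
| 50 | 4% | 2% |
| 200 (whole trial) | 1% | 1% |

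In the percent-change model, adding month-4 percent change cuts the SE by about 2-5% at 12 months and 1-3% at 18 months for pools of 25-50, and by nothing trial-wide. A separate run of the absolute-change model, with the same N, sex mix and correlations, gave 14%/10%, 7%/5%, 3%/2% and 2%/1% down the same four rows.

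The baseline must be in both arms of this comparison. Set against a model with no covariates, the cuts look larger (9-15% and 5-10% for pools of 12-50), but part of that belongs to baseline weight.

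**Step 4. In participants.** A cut c is worth 1/(1 − c)² − 1 more people. For pools of 25-50 at 12 months, 1/0.96² − 1 = 8.5% and 1/0.94² − 1 = 13%. At 18 months, 1/0.98² − 1 = 4% and 1/0.96² − 1 = 8.5%. Trial-wide, 1/0.99² − 1 = 2%.

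**Step 5. Broken pairs.** With a random pair effect and either no dropout or 20% random dropout (N = 200, ρ 0.65-0.75), the SE cuts in the absolute-change model were 7-17%, 5-9%, 1-6% and 0-3% for pools of 12, 25, 50 and 200. The worst SE ratio was 1.005, so the covariate cost no material precision in any of these settings.

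**The case against.** A reader might infer from the list of weights that the absolute-change model ignores the month-4 result and so gives up close to half of the achievable variance reduction. The documents do not support that. Section 15.3 applies the matched-pair design to both models, and the pairs are built on month-4 percent change. Month-4 weight is also not excluded: if it predicts as strongly as supposed, it is a likely choice under the significance rule.

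A reader might also take the cohorts to be closed matching pools of 10-15 and quote the largest gains. Section 7.0 gives 10-15 as the size of an intervention group session, not of a cohort or matching pool. A pool of 12 split within pairs gives 12/2 = 6 per arm, below that session size unless pools are merged; one full group per arm needs 20-30 people. On the other side, pairing across the whole trial would make early participants wait until the last cohort finished the core phase. Intermediate pools are therefore plausible, but the documents do not settle it.

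Nor do chance month-4 differences within pairs amount to bias, since assignment within the pair is random. Finally, the affected model is the second of two. The first, in percent change, matches the stated 7% versus 5% hypothesis and gains less.

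These points limit the size of the gain. They do not remove the case for pre-specifying the covariate, because whether the strongest available pre-randomisation predictor enters the models is still left to a data-driven screen.

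**Conclusion.** The point holds as a small, low-cost improvement. By rule, the month-4 result enters Aim 2 only through the pairs, and adding it as a covariate would recover what imperfect matching leaves behind. The likely gain is single-digit: about 4-6% of the standard error at 12 months and 2-4% at 18 months in the absolute-change model for pools of 25-50, and somewhat less in the percent-change model. It is about 1% or nil if matching is trial-wide, and reaches about 14% and 9% only for pools near 12. These figures rest on an assumed N, sex mix, SDs, correlations and pool size, so no gain in power can be stated. The validity of the randomised comparison is not in question.

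**What to change.** In section 15.3, keep the pair term in both models and add, as fixed pre-specified covariates:

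- in the absolute-change model, 4-month weight together with baseline weight;
- in the percent-change model, 4-month percent change.

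State that these are retained whatever their significance, and that the selection rule applies only to other covariates. Add one sentence in section 8.0 on the matching pool and how close a match must be, and one in section 15.3 on how unpaired participants and those whose partner is lost are analysed. In a mixed model with a random pair effect, the covariate keeps the month-4 information for those people.

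The cost is a few lines of SAP text. No new data are needed, because nobody can be matched on percent change without a 4-month weight.
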